**SECTION C - PREVIOUS DONATION AND HIV TESTING**

C1. Before your recent donation, have you ever donated blood? (Choose one)

- 0 No **Skip to C4**
- 1 Yes
- 97 Don't Know
- 98 Refuse to Answer

C2. Before your recent donation, how many times have you donated blood? (Choose one)

- 1 1 time
- 2 2 or more times
- 97 Don't Know
- 98 Refuse to Answer

C3. At the time of your donation, were you given information about who should not donate blood?  
(Check all that apply)

- 0 No
- 1 Yes, written information (pamphlets)
- 2 Yes, through discussion with the donor staff at the donation centre
- 97 Don't Know
- 98 Refuse to Answer

C4. Do you know of places in your community where you can be tested free of charge for HIV?

- 0 No
- 1 Yes
- 97 Don't Know
- 98 Refuse to Answer

C5. Not including HIV testing conducted as part of blood donation, have you ever been tested for HIV?  
(Choose one)

- 0 No ***Skip to instruction before D1***
- 1 Yes
- 97 Don't Know
- 98 Refuse to Answer

C6. Not including HIV testing conducted as part of blood donation, how many times have you been tested for HIV? (Choose one)

- 0 Never
- 1 1 time
- 2 2 or more times
- 97 Don't Know
- 98 Refuse to Answer

C7a. Not including HIV testing done as part of blood donation, what was the primary reason for the most recent HIV test? (Choose one)

- 1 Pregnancy care
- 2 Health insurance

- 3 Doctor's order, routine medical care, hospitalisation or surgery
- 4 I wanted to know my HIV status
- 5 Other
- 97 Don't Know
- 98 Refuse to Answer

***If C7a is not equal to 5, then skip to C8a.***

C7b. Please tell us the reason for the HIV test.

-----

C8a. Not including HIV testing done as part of blood donation, where else have you been tested for HIV? (Choose one)

- 1 General Practitioner
- 2 Local clinic / health facility
- 3 Hospital
- 4 HIV Testing Centre (known as a Voluntary Counseling and Testing or VCT Centre)
- 5 Other test site
- 97 Don't Know
- 98 Refuse to Answer

***If C8a is not equal to 5, then skip to Section D.***

C8b. Please tell us the other test site.

-----

**SECTION D - INCENTIVES AND MOTIVATIONS FOR DONATING**

**READ and HEARD:** *The following questions will ask you about things that you may do in your daily life.*

D1. Apart from your involvement in blood donation, do you do any volunteer work for any clubs, groups, societies or religious groups in your community?

- 0 No
- 1 Yes
- 97 Don't Know
- 98 Refuse to Answer

**READ and HEARD:** *The following questions will ask you about factors that may have influenced your decision to donate blood. Use the following scale to indicate how much the factors influenced your decision to donate blood. 1- Not at all, 2 - Very little, 3 - Somewhat, 4 - Very much*

D2a. My decision to donate blood was influenced by my desire to anonymously help someone else who needs blood. (Choose one)

- 1 Not at all
- 2 Very little
- 3 Somewhat
- 4 Very much
- 97 Don't Know
- 98 Refuse to Answer

D2b. My decision to donate blood was influenced by my desire to help a friend or relative who is sick or needs blood. (Choose one)

- 1 Not at all
- 2 Very little
- 3 Somewhat
- 4 Very much
- 97 Don't Know
- 98 Refuse to Answer

D2c. My decision to donate blood was influenced by a campaign on TV or radio. (Choose one)

- 1 Not at all
- 2 Very little
- 3 Somewhat
- 4 Very much
- 97 Don't Know
- 98 Refuse to Answer

D2d. My decision to donate blood was influenced by a telephone call or sms (text message) from the blood bank asking me to donate. (Choose one)

- 1 Not at all
- 2 Very little
- 3 Somewhat
- 4 Very much
- 97 Don't Know
- 98 Refuse to Answer

D2e. My decision to donate blood was influenced by my belief that it is important to give blood.  
(Choose one)

- 1 Not at all
- 2 Very little
- 3 Somewhat
- 4 Very much
- 97 Don't Know
- 98 Refuse to Answer

D2f. My decision to donate blood was influenced by my desire to get my blood test results. (Choose one)

- 1 Not at all
- 2 Very little
- 3 Somewhat
- 4 Very much
- 97 Don't Know
- 98 Refuse to Answer

D2g. My decision to donate blood was influenced by my belief that my blood type is in high demand. (Choose one)

- 1 Not at all
- 2 Very little
- 3 Somewhat
- 4 Very much
- 97 Don't Know
- 98 Refuse to Answer

D2h. My decision to donate blood was influenced by my belief that I am doing something important for society. (Choose one)

- 1 Not at all
- 2 Very little
- 3 Somewhat
- 4 Very much
- 97 Don't Know
- 98 Refuse to Answer

D2i. My decision to donate blood was influenced by my belief that I may need blood myself someday.  
(Choose one)

- 1 Not at all
- 2 Very little
- 3 Somewhat
- 4 Very much
- 97 Don't Know
- 98 Refuse to Answer

D2j. My decision to donate blood was influenced by my belief that blood donation is good for my health. (Choose one)

- 1 Not at all
- 2 Very little
- 3 Somewhat
- 4 Very much
- 97 Don't Know
- 98 Refuse to Answer

D2k. My decision to donate blood was influenced by my desire to know about my health and blood donation is a good way to find this out. (Choose one)

- 1 Not at all
- 2 Very little
- 3 Somewhat
- 4 Very much
- 97 Don't Know
- 98 Refuse to Answer

D2l. My decision to donate blood was influenced by someone offering me an incentive to donate. (Choose one)

- 1 Not at all
- 2 Very little
- 3 Somewhat
- 4 Very much
- 97 Don't Know
- 98 Refuse to Answer

D2m. My decision to donate blood was influenced by my belief that blood banks always need blood and so donating is the right thing to do. (Choose one)

- 1 Not at all
- 2 Very little
- 3 Somewhat
- 4 Very much
- 97 Don't Know
- 98 Refuse to Answer

D2n. My decision to donate blood was influenced by pressure to donate that I received from other people (such as friends, family, colleagues, fellow students, church or temple members).

- 1 Not at all
- 2 Very little
- 3 Somewhat
- 4 Very much
- 97 Don't Know
- 98 Refuse to Answer

D2o. Is there another reason that best explains why you came to donate? (Choose one)

- 0 No **Skip to D3**
- 1 Yes
- 97 Don't Know **Skip to D3**
- 98 Refuse to Answer **Skip to D3**

D2p. What is the reason that best explains why you came to donate?

-----

D3. Some people feel they must donate blood because family, friends, co-workers or other people in an organization they know donate or encourage others to donate blood. Did this happen to you when you last donated blood? (Choose one)

- 0 No
- 1 Yes
- 97 Don't Know
- 98 Refuse to Answer

D4. Do you believe that the blood service uses better HIV tests than are available at other places? (Choose one)

- 0 No
- 1 Yes
- 97 Don't Know
- 98 Refuse to Answer

D5. Did you donate blood mainly because you wanted to be tested for HIV? (Choose one)

- 0 No **Skip to D8**
- 1 Yes
- 97 Don't Know
- 98 Refuse to Answer

D6. What were all the factors that contributed to your decision to come to the blood centre to be tested for HIV? Please check all the boxes that apply to your answer. When you have selected all of your answers, please touch the "Next Question" box. (Check all the answers that apply)

- a  Only place I know of that offers HIV testing
- b  HIV testing is free
- c  HIV testing is confidential
- d  HIV testing is more accurate than at other sites
- e  HIV testing is more convenient than at other test sites
- f  Other reason
- e  Don't Know
- g  Refuse to Answer

**If D6\_f is equal to 0, then skip to D8.**

D7. Please specify other reason

-----

D8. Did you donate blood mainly because you wanted to be tested for hepatitis? (Choose one)

- 0 No **Skip to D11**
- 1 Yes
- 97 Don't Know
- 98 Refuse to Answer

D9. What were all the factors that contributed to your decision to come to the blood centre to be tested for hepatitis? Please check all the boxes that apply to your answer. When you have selected all of your answers, please touch the "Next Question" box. (Check all that apply)

- Only place I know of that offers Hepatitis testing
- Hepatitis testing is free
- Hepatitis testing is confidential
- Hepatitis testing is more accurate than at other sites
- Hepatitis testing is more convenient than at other sites
- Other reason
- Don't Know
- Refuse to Answer

***If D9\_f is equal to 0, then skip to D13.***

D10. Please specify other reason

-----

D11. Did a health worker such as a doctor, nurse, or someone from a clinic suggest that you go to the blood centre for a blood test for HIV, hepatitis, or for some other reason? (Choose one)

- 0 No ***Skip to instruction before D13***
- 1 Yes
- 97 Don't Know
- 98 Refuse to Answer

D12. Please tell us who suggested you come to the blood service for a blood test? (Choose one)

- 1 Doctor
- 2 Nurse
- 3 Someone else from the clinic
- 4 Other
- 97 Don't Know
- 98 Refuse to Answer

**READ and HEARD: Now we will ask a few questions about what you think about HIV and HBV risks and donating: In the following section, please indicate whether you think each statement is true or false.**

D13. You can donate blood if you have engaged in risk behaviors for HIV/AIDS because the blood service tests all blood and throws away any infected blood. (Choose one)

- 1 True
- 2 False
- 97 Don't Know
- 98 Refuse to Answer

D14. You can donate blood even if you engage in risk behaviors for HIV/AIDS as long as you have a negative HIV test. (Choose one)

- 1 True
- 2 False
- 7 Don't Know
- 8 Refuse to Answer

D15. You can donate blood even if you engage in risk behaviors for HIV/AIDS as long as you use condoms. (Choose one)

- 1 True
- 2 False
- 97 Don't Know
- 98 Refuse to Answer

D16. The blood test for HIV identifies everyone who is infected with the virus. (Choose one)

- 1 True
- 2 False
- 97 Don't Know
- 98 Refuse to Answer

D17. The blood test for hepatitis identifies everyone who is infected with a hepatitis virus. (Choose one)

- 1 True
- 2 False
- 97 Don't Know
- 98 Refuse to Answer

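### Two Appendix 7 skip rules omit the referral items (D11–D12) for most routes through D9 and the donor-information item (C3) for first-time donors

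*Protocol*

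**What the plan says.** Protocol section 4.4.1 names Appendix 7 as the content of the risk factor questionnaire, so its printed routing is what the computer interview would follow.

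**Section D, hepatitis block.** D8 asks "Did you donate blood mainly because you wanted to be tested for hepatitis". No leads to D11. Yes, Don't Know and Refuse carry no skip and continue to D9, a tick-all list of reasons. The rule after D9 is that if item f "is equal to 0, then skip to D13". D11 begins "Did a health worker such as a doctor, nurse, or someone from a clinic suggest that you go to the blood centre" and covers a test for HIV, hepatitis or anything else. D12 follows: "Please tell us who suggested you come to the blood service for a blood test".

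**Section D, HIV block.** This has the same layout. After D6, if item f "is equal to 0, then skip to D8", which passes over only the free-text item D7.

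**Section C.** C1 asks "Before your recent donation, have you ever donated blood", and No leads to C4. The items passed over are C2, "Before your recent donation, how many times have you donated blood", and C3, "At the time of your donation, were you given information about who should not donate blood".

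**The concern.** A skip rule should remove only items that do not apply to the respondent. The D9 rule removes two that do. Nothing in D11 or D12 restricts them to donors who ticked Other reason or to donors who were not seeking a hepatitis test. Followed as printed, the rule puts the referral question to people who did not come for a hepatitis test and withholds it from most routes through the hepatitis list.

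The C1 rule rightly removes C2, which counts earlier donations. It also removes C3, and a first-time donor has a donation at which information could have been given.

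At stake is information for donor selection. Section 1 says the results may be used to improve exclusion of high-risk donors through the donor history questionnaire, and section 3 describes first-time donations as higher risk. An item that is never asked at interview cannot be recovered from the study record afterwards.

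**Working it through.** The plan gives no figure on this point. The main check is a trace of the printed routing.

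**Hepatitis block.** The D9 options carry no letters. By the order used in D6, item f is the sixth option, Other reason.

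- D8 = No: go to D11. Referral is asked.
- D8 = Yes, Don't Know or Refuse, and Other reason ticked: D10, then D11. Referral is asked.
- D8 = Yes, Don't Know or Refuse, and Other reason not ticked (including those who mark Don't Know or Refuse at D9): go to D13. D10, D11 and D12 are not asked.

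**Comparison with the HIV block.** When Other reason is unticked at D6, the target is D8, the item directly after the free text D7. The counterpart after D9 is the item directly after the free text D10, which is D11. The printed target is two items further on. A second sign of a slip is that D11 = No leads to the instruction before D13, whereas the D9 rule names D13 itself and so, read literally, also misses the introduction to the true/false items.

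**Section C.**

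- C1 = No: go to C4. C2 and C3 are not asked.
- C1 = Yes, Don't Know or Refuse: no skip, so C3 is asked.

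C3 is therefore missing for every donor who reports no earlier donation, yet it is put to those who do not know or refuse to say.

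**Possible size for D11.** The protocol gives none of the shares needed, so all inputs here are assumptions. Let s be the share of donors who reach D9, u the share of those who leave Other reason unticked, r1 the referral prevalence among those who reach D9, and r0 the prevalence among the rest.

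- True prevalence = s·r1 + (1 − s)·r0
- Prevalence among those asked = [s(1 − u)·r1 + (1 − s)·r0] / (1 − s·u)

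Larger case: s = 5%, u = 80%, r1 = 30%, r0 = 2%.

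- True: 0.05 × 0.30 + 0.95 × 0.02 = 0.034
- Asked: (0.01 × 0.30 + 0.95 × 0.02) / 0.96 = 0.022 / 0.96 = 0.0229
- Relative loss: 1 − 0.0229 / 0.034 = about 33%

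Smaller case: s = 1%, u = 80%, r1 = 10%, r0 = 2%.

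- True: 0.01 × 0.10 + 0.99 × 0.02 = 0.0208
- Asked: (0.002 × 0.10 + 0.99 × 0.02) / 0.992 = 0.0200 / 0.992 = 0.0202
- Relative loss: 1 − 0.0202 / 0.0208 = about 3%

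Both figures concern the marginal prevalence of referral. Neither is an effect on a case-control odds ratio.

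**The case against.** The strongest reply is that little of scientific weight is lost. D11, D12 and C3 are not among the hypothesised risk factors in section 4 or the named predictors in section 4.9. At most they fall under the other possible predictors to be examined. Test-seeking itself is still recorded for everyone through D2f, D2k, D5 and D8. The same routing applies to cases and controls. All of this stands, and it limits the point to a correction of the instrument.

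The reply is also fair on C3. Section C is headed as dealing with previous donation, C3 follows two items on earlier donations, and it says only your donation where C1 and C2 say your recent donation. The skip could be deliberate. Against that, the questionnaire regularly uses your donation for the index donation, and Section G explains its reference period by the most recent one. The index reading is the likelier, but the text does not settle it.

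A third reply is that Appendix 7 is visibly unfinished. It has a placeholder for the OMB number and an author's query at J14a, and section 4.11 still schedules ACASI development and pilot testing. That lowers the severity but does not make the D9 target right.

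A reader might infer more than the protocol supports:

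- *That referral is lost in the donors most likely to report it.* Nothing says hepatitis test-seekers are referred most often. D11 also covers referral for HIV testing, and HIV test-seekers who answer No to D8 still reach it.
- *That a third of referrals would be missed.* That is one assumed case; another gives about 3%.
- *That imputation would be biased.* Section 4.9 plans a nonresponse analysis followed by weighting and/or multiple imputation, and does not say that items skipped by routing would be imputed. For D11, some who reach D9 are observed. For C3, no donor answering No to C1 is observed, so any imputation would have to borrow from the others. That matters only if C3 concerns the index donation.
- *That the main risk-factor results are affected.* No effect on any odds ratio has been shown.

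**Conclusion.** The D9 rule is wrong as printed. It conflicts with the matching HIV rule and with the D8 = No route, and it leaves D11 and D12 structurally missing for everyone who reaches D9 without ticking Other reason. This rests only on the printed routing and on reading D9_f as the sixth option.

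The C1 rule leaves C3 structurally missing for all donors who report no earlier donation. Whether the skip or the wording of C3 is at fault depends on which donation C3 means. One of the two needs changing.

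The loss is confined to exploratory motivation and donor-education items. The hypotheses under Objectives 1a and 1b and the power calculations are not affected. The distortion of referral prevalence cannot be sized from the protocol; 3% and 33% are the results of two assumed cases and do not bound it. The correction is worth making because it is cheap now and the answers cannot be collected later from the same records.

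**What to change.** 1. After D9, change the skip target for Other reason not ticked from D13 to D11, so that only the free-text item D10 is passed over.
2. Decide which donation C3 refers to. If it is the index donation, send C1 = No to C3, so that only C2 is skipped, and name the recent donation in C3. If it is earlier donations, keep the skip and reword C3 to say so.
3. Walk through every answer to D8, D9 and C1 in the programmed interview during the pilot test.

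The cost is one changed target after D9, either one changed target or one reworded item in Section C, and one or two extra questions for the donors affected. Design and sample size do not change. Timing matters because section 4.6 requires OMB approval of all interview instruments and allows up to nine months for it. The changes should go in before clearance and programming; the protocol does not say what a later correction would require.

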#### **Procedures for donors with incident infection identified through LAg Avidity assay (serology and NAT concordant positive, with LAg Avidity results)**

LAg avidity testing will be performed in real time along with routine SANBS supplementary testing and the test results will be available at the time of notification of positive test results. All donors with concordant results, both LAg avidity negative and positive, will initially be counseled in accordance with the SANBS standard procedures which includes the performing of an HIV rapid test when the donor returns for counseling.

The donors with an incident HIV infection identified through the LAg Avidity assay will be assessed for suitability to be enrolled on to the study. If the donor satisfies the inclusion criteria for this study, consent will be sought and the donor enrolled. Blood samples will be collected and the ACASI questionnaire completed.

All other HIV positive donors (serology only and/or non-recent concordant infections) will complete the standard SANBS HIV risk inventory survey as part of the standard SANBS operational procedure.

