**CONFIDENTIAL PERSONAL INFORMATION**

**CONFIDENTIALITY NOTE: This letter is intended only for the confidential use of the intended recipient. The information may be protected by privilege. Please note that any review, dissemination, distribution or copying of this letter is strictly prohibited if you are not the intended recipient. If you have received this letter in error, please desist from reading the contents, notify the sender immediately and destroy this letter**

<Donor's Address>

<Date>

<Donor Number>

<Dear Donor>

Thank you for your recent blood donation. The South African National Blood Service (SANBS) screens all blood donations for certain infections which may be transmitted by blood transfusion, specifically hepatitis B, hepatitis C, HIV and Syphilis. The screening tests used are sometimes over-sensitive and, although an abnormal result may be detected, this does not necessarily mean that you have, or have ever had, an infection.

On your last blood donation the results of a nucleic acid screening test (PCR) was positive. The Nucleic Acid Test is a sensitive test designed to detect early viral infections. Additional tests performed, for the above infections, were however, negative i.e. no corresponding antibodies to any of the above infections were detected.

Because of the discrepancy in these test results, you are urged to revisit a Blood Donor Centre to have another blood sample taken so that the tests can be repeated.

If this result is confirmed, you will unfortunately not be able to continue to donate blood. Because these tests are designed to detect infections which may be transmitted by blood transfusion and, since they may be sexually transmitted, neither you nor your partner may donate blood until this matter has been resolved.

Since it is possible that these results indicate a recent transmissible infection please do not donate blood until this matter is resolved. .

If you have any questions relating to this letter, please contact (MLO and contact number).

Yours sincerely,

Dr.....  
Medical Officer (SANBS)

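### Referral items D11–D12, and to a lesser extent HIV-testing items C5–C8a, are not limited to the time before the index donation, so some cases can report the study's own recall or follow-up testing as exposure

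*Protocol*

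**What the plan says.** **Referral items (Protocol, Appendix 7, Section D).** D11 asks about referral by a health worker, naming doctors and nurses as examples: did "someone from a clinic suggest that you go to the blood centre for a blood test for HIV, hepatitis, or for some other reason". D12 continues: "Please tell us who suggested you come to the blood service for a blood test", with doctor, nurse, someone else from the clinic, and other as the substantive answers. Neither item gives a time or mentions donating. The lead-in that frames this part of the section stands before D2a: "The following questions will ask you about factors that may have influenced your decision to donate blood".

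**Testing-history items (Appendix 7, Section C).** C1 is tied to the index donation: "Before your recent donation, have you ever donated blood". C2 carries the same limit. C5 does not: "Not including HIV testing conducted as part of blood donation, have you ever been tested for HIV". Nor does C7a: "Not including HIV testing done as part of blood donation, what was the primary reason for the most recent HIV test". C6 and C8a open with the same exclusion of donation testing and also have no cut-off.

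**What happens before the interview.** Under Section 4.2.1, medical liaison officers and research nurses recall donors with recent infection to the blood centre. The NAT-only letter in Appendix 1, sent in the name of a medical officer, says: "you are urged to revisit a Blood Donor Centre to have another blood sample taken so that the tests can be repeated". NAT-yield cases give confirmatory samples before consent and the ACASI. For concordant donors, initial counselling "includes the performing of an HIV rapid test when the donor returns for counseling", again before consent. Section 4.2.2 (Participant Enrollment) extends similar recall and counselling to early HBV infections. Controls complete the ACASI after donating (Section 4.2.2, Control Recruitment and Enrollment).

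**The concern.** The study's recall of a case is close to a literal instance of what D11 asks about: a nurse or doctor tells the donor to come to the blood centre for a blood test. The protocol also calls its own collection sites clinics. Cases have had this contact by the time they answer, and controls have had none for the index donation. A careful and honest case can say yes, and the contact cannot be a cause of the infection.

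In Section C, a case tested for HIV after the donation could count that test in C5 and C6. In C7a and C8a the case could then describe a later event than the one a control describes.

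Section 4.9 says that predictors other than the named ones will be examined, so these items can enter the case-control comparison. The answers carry no date. Apart from what a respondent volunteers in the free-text follow-ups to C7a and C8a, an analyst could not separate events before the donation from later ones.

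**Working it through.** The plan states no figure on this point, so there is none to reproduce. The check has two parts: wording against timing, then an illustration of size.

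**1. Wording against timing**

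| Item | Limit at index donation? | Other protection | Post-donation event left open |
|---|---|---|---|
| C1, C2 | Yes | – | None |
| C5, C6, C7a, C8a | No | Excludes HIV testing done as part of donation | Counselling-visit rapid test (concordant HIV cases); outside test after notification |
| D11, D12 | No | Section lead-in and neighbouring items only | Recall call or letter (HIV and HBV cases) |

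For C5–C8a, the exclusion plausibly covers the blood service's confirmatory retest. It does not clearly cover the rapid test, which is done at a later visit. It does not cover a test by the donor's own doctor, a route that the second letter in Appendix 1 offers. Section 4.8.1 expects about 50 NAT-only and about 160 LAg-recent HIV infections a year, so 160/(50 + 160) = 76% of expected HIV infections are of the concordant type that receives the rapid test.

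**2. Size, as illustration**

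Let the true share exposed before donation be p in both groups, so that there is no real association. Let f be the share of unexposed cases who count the later event. The protocol gives neither p nor f; both are assumed.

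- Case share: p₁ = p + (1 − p)f. Control share: p.
- Spurious odds ratio: [p₁/(1 − p₁)] / [p/(1 − p)].

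D11, p = 0.05, f = 0.05: p₁ = 0.05 + 0.95 × 0.05 = 0.0975, and OR = (0.0975/0.9025)/(0.05/0.95) = 2.05.

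The chance of a significant result uses a two-sided 5% test of two proportions with 300 cases and 900 controls, ignoring clustering and matching. For the same example:
- The pooled share is (0.0975 × 300 + 0.05 × 900)/1200 = 0.0619, so the null standard error is 0.0161. The standard error under the shifted shares is 0.0186.
- (0.0475 − 1.96 × 0.0161)/0.0186 ≈ 0.86, a probability of about 0.81.

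| Item | p | f | p₁ | Spurious OR | P(significant), 300/900 |
|---|---|---|---|---|---|
| D11 | 2% | 5% | 6.9% | 3.63 | 95% |
| D11 | 5% | 5% | 9.75% | 2.05 | 81% |
| D11 | 5% | 10% | 14.5% | 3.22 | >99% |
| D11 | 10% | 5% | 14.5% | 1.53 | 57% |
| D11 | 10% | 10% | 19% | 2.11 | 97% |
| C5 | 60% | 5% | 62% | 1.09 | 9% |
| C5 | 60% | 10% | 64% | 1.19 | 23% |
| C5 | 60% | 25% | 70% | 1.56 | 88% |

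For HBV at 150 cases and 450 controls, the D11 rows with p = 5% give 55% (f = 5%) and 94% (f = 10%).

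As a yardstick only, Table 8 gives detectable odds ratios of 1.65–1.94, derived for multiple sexual partners. For a rare exposure, a small f is enough to reach that range. For a common one it is not. With the items limited to the time before donation, and answered accordingly, f = 0 and the spurious odds ratio is 1.00 for every p.

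**The case against.** The context of D11 is the best defence. Section D is about incentives and motivations, and its lead-in concerns the decision to donate. D3 refers to the last donation, and D5 and D8 ask whether the respondent donated mainly to be tested. D6 and D9 speak of coming to the blood centre for testing when they mean donating. Many respondents will read D11 the same way. This stands as a reason to expect f well below 1. It does not bring f to zero: the lead-in introduces the rating scale used in the D2 items, and D11–D12, unlike D3, D5 and D8, drop any reference to donating. D11 is also not put to everyone, because the skip after D9 takes some respondents straight to D13.

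For C5–C8a, the exclusion of donation testing is a real safeguard, and the answer options of C7a and C8a point to reasons and places outside the blood service. Table 1 lists the rapid test as standard blood-service procedure, so some respondents will treat it as donation testing. Outside testing may be uncommon among enrolled cases, since enrolment requires return to the blood service and Section 4.2.1 directs to outside care mainly those who refuse to return. The documents give no share. Section 4.2.2 does, however, let participants complete the interview at a later date. The C5–C8a gap is therefore the smaller one and mainly concerns HIV cases.

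A reader might infer that the recall is recorded as exposure in cases generally, or that the study's main results are at risk. The documents support neither. The wording permits the misreading but does not force it. Neither referral nor HIV-testing history is among the hypotheses in Section 4 or the named predictors in Section 4.9. A reader might also infer an association for C5 as large as those the study is sized to detect; that needs an assumed f far higher than the exclusion makes likely.

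**Conclusion.** The point holds for D11–D12 and, in weaker form, for C5–C8a. As printed, some HIV and HBV cases can truthfully report the recall in D11–D12 while controls cannot, so differential misclassification is possible by procedure. For C5–C8a, only the rapid test and outside testing after notification remain open.

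The size depends on unknown p and f. With 5% true referral and 5–10% of unreferred cases counting the recall, the spurious odds ratio for D11 is about 2.1–3.2. With 60% truly tested and 5–25% of untested cases counting a later test, that for C5 is about 1.1–1.6. These are illustrations, not estimates, and the significance probabilities ignore clustering.

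The harm is confined to the motivation, test-seeking and exploratory predictor analyses. The sample size, case definitions and named hypotheses are untouched. The items should be changed because the defect can hardly be repaired after data collection and is cheap to remove before it.

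**What to change.** - **D11 and D12:** ask whether, before the recent donation, a health worker suggested going to donate in order to have a blood test, and who it was. State that the blood service's follow-up call or letter is not to be counted.
- **C5, C6, C7a and C8a:** put the limit already used in C1 and C2 in front of each item. State that any HIV test since that donation (at the recall visit, the counselling-visit rapid test, or by the respondent's own doctor or clinic) is not to be counted. Keep the existing exclusion of donation testing.

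The cost is rewording six ACASI items and re-recording their audio. Section 4.6 says the instruments still have to be approved by OMB, so the change belongs before that clearance. It adds no items, visits or participants, and alters no sample-size or power figure.
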